NCT number: NCT05683158

Research protocol (Human subject study)

Research project title

[figure not shown]
Compensatory kinematic analysis in various directions after chronic stroke

Methodology and Design

The inclusion criteria for the participants with stroke were physician-confirmed chronic hemiplegia (≥ 6 months onset), Mini-Mental State Examination ≥ 25 , Modified Ashworth Scale (MAS) (biceps ≤ 2 , triceps ≤ 2), ability to sit alone on a chair, and FMA upper extremities score ≥ 21 . The healthy participants were individuals without any history of neurological or orthopedic diseases.

[figure not shown]
- The exclusion criteria were muscle flaccidity, neglect syndrome, orthopaedic diseases, and poor coordination.

* The specific placement of markers

- Sternum, xyphoid process, Both acromion, C7, T4, elbow(lateral and medial epicondyle), wrist (lateral and medial styloid process), finger 3rd MCP

The seated reaching task posture is as follows:

- The participant attempts to reach the target using the affected upper limb
- The seated height is adjusted to 100% of the participant's lower limb length, with the feet flat on the floor and the knees bent at a 90 degree angle. A chair with adjustable height is used to achieve this.
- Reaching movements are categorized into three directions: forward, ipsilateral and contralateral direction.
- The task is performed five times in a comfortable speed for each direction, and for analysis purposes, three out of the five trials are selected to calculate the average time.

1. Clinical assessment

1-1. Fugl-Meyer motor Assessment of the Lower Extremity (FMA-UE) Assessment of sensorimotor function:

A. UPPER EXTREMITY, sitting position				
I. Reflex activity				
Flexors: biceps and finger flexors (at least one)	0	2		
Extensors: triceps	0	2		
Subtotal I (max 4)				
II. Volitional movement within synergies, without gravitational help				
Flexor synergy: Hand from contralateral knee to ipsilateral ear. From extensor synergy (shoulder adduction/ internal rotation, elbow extension, forearm pronation) to flexor synergy (shoulder abduction/ external rotation, elbow flexion, forearm supination).	Shoulder Elbow Forearm	retraction elevation abduction (90°) external rotation flexion supination		
Extensor synergy: Hand from ipsilateral ear to the contralateral knee	Shoulder Elbow Forearm	adduction/internal rotation extension pronation		
Subtotal II (max 18)				
III. Volitional movement mixing synergies, without compensation				
Hand to lumbar spine hand on lap	cannot perform or hand in front of ant-sup iliac spine hand behind ant-sup iliac spine (without compensation) hand to lumbar spine (without compensation)			
Shoulder flexion 0° - 90° elbow at 0° pronation-supination 0°	immediate abduction or elbow flexion abduction or elbow flexion during movement flexion 90°, no shoulder abduction or elbow flexion			
Pronation-supination elbow at 90° shoulder at 0°	no pronation/supination, starting position impossible limited pronation/supination, maintains starting position full pronation/supination, maintains starting position			
Subtotal III (max 6)				
IV. Volitional movement with little or no synergy				
Shoulder abduction 0 - 90° elbow at 0° forearm neutral	immediate supination or elbow flexion supination or elbow flexion during movement abduction 90°, maintains extension and pronation			
Shoulder flexion 90° - 180° elbow at 0° pronation-supination 0°	immediate abduction or elbow flexion abduction or elbow flexion during movement flexion 180°, no shoulder abduction or elbow flexion			
Pronation/supination elbow at 0° shoulder at 30° - 90° flexion	no pronation/supination, starting position impossible limited pronation/supination, maintains start position full pronation/supination, maintains starting position			
Subtotal IV (max 6)				
V. Normal reflex activity assessed only if full score of 6 points is achieved in part IV; compare with the unaffected side				
Biceps, triceps, finger flexors	2 of 3 reflexes markedly hyperactive 1 reflex markedly hyperactive or at least 2 reflexes lively maximum of 1 reflex lively, none hyperactive			
Subtotal V (max 2)				
Total A (max 36)				

B. WRIST support may be provided at the elbow to take or hold the starting position, no support at wrist, check the passive range of motion prior testing		none	partial	full
Stability at 15° dorsiflexion elbow at 90°, forearm pronated shoulder at 0°	less than 15° active dorsiflexion dorsiflexion 15°, no resistance tolerated maintains dorsiflexion against resistance	0	1	2
Repeated dorsiflexion / volar flexion elbow at 90°, forearm pronated shoulder at 0°, slight finger flexion	cannot perform volitionally limited active range of motion full active range of motion, smoothly	0	1	2
Stability at 15° dorsiflexion elbow at 0°, forearm pronated slight shoulder flexion/abduction	less than 15° active dorsiflexion dorsiflexion 15°, no resistance tolerated maintains dorsiflexion against resistance	0	1	2
Repeated dorsiflexion / volar flexion elbow at 0°, forearm pronated slight shoulder flexion/abduction	cannot perform volitionally limited active range of motion full active range of motion, smoothly	0	1	2
Circumduction elbow at 90°, forearm pronated shoulder at 0°	cannot perform volitionally jerky movement or incomplete complete and smooth circumduction	0	1	2
Total B (max 10)				

C. HAND support may be provided at the elbow to keep 90° flexion, no support at the wrist, compare with unaffected hand, the objects are interposed, active grasp		none	partial	full
Mass flexion from full active or passive extension		0	1	2
Mass extension from full active or passive flexion		0	1	2
GRASP				
a. Hook grasp flexion in PIP and DIP (digits II-V), extension in MCP II-V	cannot be performed can hold position but weak maintains position against resistance	0	1	2
b. Thumb abduction 1-st CMC, MCP, IP at 0°, scrap of paper between thumb and 2-nd MCP joint	cannot be performed can hold paper but not against tug can hold paper against a tug	0	1	2
c. Pincer grasp, opposition pulpa of the thumb against the pulpa of 2-nd finger, pencil, tug upward	cannot be performed can hold pencil but not against tug can hold pencil against a tug	0	1	2
d. Cylinder grasp cylinder shaped object (small can) tug upward, opposition of thumb and fingers	cannot be performed can hold cylinder but not against tug can hold cylinder against a tug	0	1	2
e. Spherical grasp fingers in abduction/flexion, thumb opposed, tennis ball, tug away	cannot be performed can hold ball but not against tug can hold ball against a tug	0	1	2
Total C (max 14)				

D. COORDINATION/SPEED , sitting, after one trial with both arms, eyes closed, tip of the index finger from knee to nose, 5 times as fast as possible		marked	slight	none
Tremor		0	1	2
Dysmetria	pronounced or unsystematic slight and systematic no dysmetria	0	1	2
		≥ 6s	2 - 5s	< 2s
Time start and end with the hand on the knee	6 or more seconds slower than unaffected side 2-5 seconds slower than unaffected side less than 2 seconds difference	0	1	2
Total D (max 6)				

1-2 TIS

Item

Static sitting balance	
1	Starting position Patient falls or cannot maintain starting position for 10 seconds without arm support  0
	Patient can maintain starting position for 10 seconds  2
	If score = 0, then TIS total score = 0
2	Starting position Therapist crosses the unaffected leg over the hemiplegic leg Patient falls or cannot maintain sitting position for 10 seconds without arm support  0
	Patient can maintain sitting position for 10 seconds  2
3	Starting position Patient crosses the unaffected leg over the hemiplegic leg Patient falls  0 Patient cannot cross the legs without arm support on bed or table  1 Patient crosses the legs but displaces the trunk more than 10 cm backwards or assists crossing with the hand  2 Patient crosses the legs without trunk displacement or assistance  3 Total static sitting balance  7
Dynamic sitting balance	
1	Starting position Patient is instructed to touch the bed or table with the hemiplegic elbow (by shortening the hemiplegic side and lengthening the unaffected side) and return to the starting position Patient falls, needs support from an upper extremity or the elbow  0 does not touch the bed or table  1 Patient moves actively without help, elbow touches bed or table  1 If score = 0, then items 2 and 3 score 0
2	Repeat item 1 Patient demonstrates no or opposite shortening/lengthening  0 Patient demonstrates appropriate shortening/lengthening  1 If score = 0, then item 3 scores 0
3	Repeat item 1 Patient compensates. Possible compensations are: (1) use of upper extremity, (2) contralateral hip abduction, (3) hip flexion (if elbow touches bed or table further than proximal half of femur), (4) knee flexion, (5) sliding of the feet Patient moves without compensation  1
4	Starting position Patient is instructed to touch the bed or table with the unaffected elbow (by shortening the unaffected side and lengthening the hemiplegic side) and return to the starting position Patient falls, needs support from an upper extremity or the elbow  0 does not touch the bed or table  1 Patient moves actively without help, elbow touches bed or table  1 If score = 0, then items 5 and 6 score 0
5	Repeat item 4 Patient demonstrates no or opposite shortening/lengthening  0 Patient demonstrates appropriate shortening/lengthening  1 If score = 0, then item 6 scores 0

Item

6	Repeat item 4	Patient compensates. Possible compensations are: (1) use of upper extremity, (2) contralateral hip abduction, (3) hip flexion (if elbow touches bed or table further than proximal half of femur), (4) knee flexion, (5) sliding of the feet Patient moves without compensation	 0  1
7	Starting position Patient is instructed to lift pelvis from bed or table at the hemiplegic side (by shortening the hemiplegic side and lengthening the unaffected side) and return to the starting position	Patient demonstrates no or opposite shortening/lengthening Patient demonstrates appropriate shortening/lengthening If score = 0, then item 8 scores 0	 0  1
8	Repeat item 7	Patient compensates. Possible compensations are: (1) use of upper extremity, (2) pushing off with the ipsilateral foot (heel loses contact with the floor) Patient moves without compensation	 0  1
9	Starting position Patient is instructed to lift pelvis from bed or table at the unaffected side (by shortening the unaffected side and lengthening the hemiplegic side) and return to the starting position	Patient demonstrates no or opposite shortening/lengthening Patient demonstrates appropriate shortening/lengthening If score = 0, then item 10 scores 0	 0  1
10	Repeat item 9	Patient compensates. Possible compensations are: (1) use of upper extremities, (2) pushing off with the ipsilateral foot (heel loses contact with the floor) Patient moves without compensation	 0  1
		Total dynamic sitting balance	/10

Co-ordination

1	Starting position Patient is instructed to rotate upper trunk 6 times (every shoulder should be moved forward 3 times), first side that moves must be hemiplegic side, head should be fixated in starting position	Hemiplegic side is not moved three times Rotation is asymmetrical Rotation is symmetrical If score = 0, then item 2 scores 0	 0  1  2
2	Repeat item 1 within 6 seconds	Rotation is asymmetrical Rotation is symmetrical	 0  1
3	Starting position Patient is instructed to rotate lower trunk 6 times (every knee should be moved forward 3 times), first side that moves must be hemiplegic side, upper trunk should be fixated in starting position	Hemiplegic side is not moved three times Rotation is asymmetrical Rotation is symmetrical If score = 0, then item 4 scores 0	 0  1  2
4	Repeat item 3 within 6 seconds	Rotation is asymmetrical Rotation is symmetrical Total co-ordination	 0  1 /6
	Total Trunk Impairment Scale		

1-3 PASS

Maintaining a Posture

Give the subject instructions for each item as written below. When scoring the item, record the lowest response category that applies for each item.

1. Sitting Without Support

Examiner: Have the subject sit on a bench/mat without back support and with feet flat on the floor.

- (3) Can sit for 5 minutes without support
- (2) Can sit for more than 10 seconds without support
- (1) Can sit with slight support (for example, by 1 hand)
- (0) Cannot sit

2. Standing With Support

Examiner: Have the subject stand, providing support as needed. Evaluate only the ability to stand with or without support. Do not consider the quality of the stance.

- (3) Can stand with support of only 1 hand
- (2) Can stand with moderate support of 1 person
- (1) Can stand with strong support of 2 people
- (0) Cannot stand, even with support

3. Standing Without Support

Examiner: Have the subject stand without support. Evaluate only the ability to stand with or without support. Do not consider the quality of the stance.

- (3) Can stand without support for more than 1 minute and simultaneously perform arm movements at about shoulder level
- (2) Can stand without support for 1 minute or stands slightly asymmetrically
- (1) Can stand without support for 10 seconds or leans heavily on 1 leg
- (0) Cannot stand without support

4. Standing on Nonparetic Leg

Examiner: Have the subject stand on the nonparetic leg. Evaluate only the ability to bear weight entirely on the nonparetic leg. Do not consider how the subject accomplishes the task.

- (3) Can stand on nonparetic leg for more than 10 seconds
- (2) Can stand on nonparetic leg for more than 5 seconds
- (1) Can stand on nonparetic leg for a few seconds
- (0) Cannot stand on nonparetic leg

5. Standing on Paretic Leg

Examiner: Have the subject stand on the paretic leg. Evaluate only the ability to bear weight entirely on the paretic leg. Do not consider how the subject accomplishes the task.

- (3) Can stand on paretic leg for more than 10 seconds
- (2) Can stand on paretic leg for more than 5 seconds
- (1) Can stand on paretic leg for a few seconds
- (0) Cannot stand on paretic leg

Maintaining Posture SUBTOTAL _____

Safety evaluation criteria and evaluation methods

Before starting the experiments, the health and physical condition of the subjects are assessed, and within 24 hours after the experiment, and signs of physical abnormalities are monitored.

Data analysis and statistical methods

To determine the sample size, the G * Power V.3.1 was utilized (Franz Paul, Kiel, Germany) (Faul F et al., 2007) incorporating an effect size of 0.44, $\alpha < 0.05$, power = 0.80, requiring total sample size of 12 participants (Dos Santos et al., 2019).

1. Statistical analysis was performed with IBM SPSS (version 28.0.1.1 (14)). Data were tested for normality using the Kolmogorov-Smirnov test. Kinematic data did not significantly deviate from a normal distribution ($P > 0.05$). The Chi-square test was used to assess the sex distribution of the participants. The independent *t*-test and Mann-Whitney *U* test, as a nonparametric test, were employed to compare the two groups concerning specific demographic and clinical characteristics.

In the event of an unforeseen emergency, the participant's condition will be assessed, and immediate contact

Predicted side effects and precautions with corresponding measures

will be made with emergency medical personnel for necessary actions. Subsequently, a prompt report will be submitted to the Institutional Review Board (IRB)

Criteria for discontinuation and dropout

1. Inability to independently perform the action of sitting and extending the paralyzed arm
2. Feeling of dizziness

Risks and benefits to research participants

- Prior to the start of the experiment, participants will receive a comprehensive explanation of the entire experimental procedure and the potential risks involved through an informed consent document. They will proceed with the experiment after understanding and acknowledging these risks.

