Official Title:

Compensatory Kinematic Movements in Various Directions After Stroke

NCT Number:

NCT05683158

Document Date:

July 19, 2022

Statistical Analysis

Statistical analyses were performed using various methods to comprehensively evaluate the data. For comparing demographic and clinical characteristics between the two groups, both chi-square test and t-test were employed.

The main analysis utilized two-way mixed-design analyses of variance, conducted independently for each variable. This analysis incorporated three levels as the within-subject factor and the participant group (healthy, stroke) as the between-subject factor. To account for multiple comparisons, Bonferroni post-hoc tests were performed. All statistical analyses were conducted using a significance level (α) of $p < 0.05$.

Sample size determination was carried out using G*Power V.3.1 software (Franz Paul, Kiel, Germany) (Faul et al., 2007). The calculation parameters included an effect size (d) of 1.9, significance level (α) ≤ 0.05 , power = 0.8, and type II error (β) = 0.2, following the methodology of previous research (Machado et al., 2019).

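### The protocol averages three of five reaching trials with no stated selection rule or blinding; analyse all valid trials instead, under a closed exclusion list

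*Protocol*

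**What the plan says.** The protocol's seated reaching task (Methodology and Design) sets three directions: "Reaching movements are categorized into three directions: forward, ipsilateral and contralateral direction". For repetitions it says "The task is performed five times in a comfortable speed for each direction", and then "for analysis purposes, three out of the five trials are selected to calculate the average time". That is all either document says about trials. No rule, selector, timing or blinding is given, and the sentence covers only time.

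The SAP's main analysis is "two-way mixed-design analyses of variance, conducted independently for each variable", with a three-level within-subject factor and "the participant group (healthy, stroke) as the between-subject factor". The SAP does not name the three levels; I take them to be the directions. It does not say how many trials make up a participant's value, or whether variables other than time use the same three.

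The protocol asks the participant to attempt to reach the target, but neither document says how an unsuccessful attempt is handled. The first criterion under Criteria for discontinuation and dropout (inability to sit and extend the arm independently) concerns the participant, not a single trial.

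**The concern.** The value entering the ANOVA for each participant and direction depends on which three reaches are kept. There are C(5,3) = 10 possible sets per direction, and 10 × 10 × 10 = 1,000 combinations over three directions. If someone who knows the group or has seen the times makes the choice, the result can follow the choice.

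Two of five performed trials are also discarded. That all five were recorded is my inference from their being performed and then selected from. Unsuccessful reaches are more likely in the stroke group, so leaving their treatment open matters most there.

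All three ANOVA effects are potentially exposed (group, direction and their interaction), but each under a different condition. The working separates them.

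**Working it through.** **1. The plan's own figure.** The only computed design figure is the protocol's total of 12. It does not depend on trial selection.
- Protocol, "incorporating an effect size of 0.44": the metric is not named. I take it as Cohen's f for a within-between interaction with 2 groups, 3 measures, correlation 0.5 and sphericity. Then λ = f²·N·m/(1 − ρ) = 0.1936 × 12 × 3 / 0.5 = 13.9 on 2 and 20 df, giving power 0.88. Twelve is the smallest even N reaching 0.80.
- SAP, "The calculation parameters included an effect size (d) of 1.9": a two-sided t-test with 6 per group has power 0.84, again a total of 12.

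I therefore use 12, assuming an equal split of 6 per group.

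**2. Precision.** For independent trials with variance σ², the mean of k arbitrary trials has error variance σ²/k: 0.33σ² for three and 0.20σ² for five. This needs no distributional assumption. The next two results assume normal trials.
- The expected order statistics of five are −1.163, −0.495, 0, 0.495 and 1.163. The lowest three average (−1.163 − 0.495 + 0)/3 = −0.553, so keeping the fastest or slowest three moves a participant's mean by about 0.55 trial SD.
- The middle three by rank have variance 0.23σ².

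With lognormal times at CV 0.5, the shifts are about −0.53 (fastest) and +0.48 (slowest). The middle-three variance is then about 0.19σ², and the middle-three mean sits about 0.12 SD low.

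**3. Effect on the planned ANOVA.** The documents give no trial SDs, so everything here is illustrative. Model: 6 per group, 3 directions, 5 trials, normal errors, 40,000 runs per cell, and the SAP's criterion, "All statistical analyses were conducted using a significance level (α) of $p < 0.05". Between-subject SD is 1 per direction, made up of shared SD √0.75 and subject-by-direction SD 0.5. Simulation error is about 0.1 point (√(0.05 × 0.95/40,000) = 0.0011).

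Group effect, healthy trial SD 0.3:

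| Stroke trial SD | 0.3 | 0.45 | 0.6 | 0.9 |
|---|---|---|---|---|
| Type I error, all five | 5.0% | 4.9% | 5.1% | 4.8% |
| Type I error, fastest three | 5.0% | 5.0% | 6.0% | 8.5% |
| Power at difference 1.0, all five | 40% | 40% | 40% | 39% |
| Same, arbitrary three | 40% | 40% | 40% | 39% |
| Same, fastest three | 40% | 35% | 29% | 20% |
| Same, slowest three | 40% | 46% | 51% | 61% |

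The last column reflects a false group shift of 0.553 × (0.9 − 0.3) = 0.33. Opposite selection (fastest in one group, slowest in the other) at equal SD 0.3 gives the same shift, 2 × 0.553 × 0.3 = 0.33, and a type I error of about 9%.

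Direction and interaction, fastest three:

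| Trial SD by direction | Direction type I error | Interaction type I error |
|---|---|---|
| Equal across directions within each group | about 5% | about 5% |
| 0.3 / 0.6 / 0.9 in both groups | about 19% | about 5% |
| 0.3 / 0.6 / 0.9 in stroke only | about 9% | about 8.7% |

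With all five trials, both are about 5% in the two unequal-SD settings.

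**4. Other variables.** If trials are chosen by time, a variable with within-person correlation r to time shifts by 0.553r of its own trial SD: 0.17, 0.28 and 0.39 for r = 0.3, 0.5 and 0.7.

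**The case against.** Taking three of five trials is ordinary in movement analysis, and the gap may be one of reporting only. A rule fixed in advance, such as the first three or the middle three by rank, keeps type I error at about 5%. A neutral choice costs almost no power. With one common rule and equal trial SDs across directions, the group type I error stays at or below 6% unless stroke trial SD exceeds twice the healthy value (8.5% at three times). All of this stands, and it limits the size of the point. It does not supply the missing rule.

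Three stronger readings are tempting, and the documents do not support them.
- **That trials were chosen to favour a result.** Nothing in either document indicates this; the text only leaves room for it. Choosing the slowest three in stroke and the fastest three in healthy participants would give a group type I error of 34% in a single-direction t-test if half the single-trial variance lay within participants (9% if a tenth did). That is a worst case the wording allows, not a description of the study.
- **That any variation of trial SD across directions threatens the interaction.** It does so only if the pattern differs between groups. When both groups share it, both shift alike and the interaction stays nominal; the direction main effect is the one exposed.
- **That discarding two trials materially weakens the study.** The loss is at most about one point of power in these settings.

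Using all valid trials also has a weakness. Missed reaches have no movement time, so leaving them out of the mean is itself outcome-related and can flatter the stroke group. The fix has to address this.

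**Conclusion.** The point holds as a should-fix item. That no selection rule or blinding is stated, and that the SAP is silent on trials, is certain from the text. The size of any bias is not known: it depends on how the three were chosen and on trial SDs that the documents do not give.

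Under the assumed SDs, non-neutral selection takes a 5% test to about 8.5–9% for group (unequal trial SD, or opposite selection), up to about 19% for direction (trial SD differing across directions), and about 8.7% for the interaction (only if that pattern differs by group). With neutral selection there is no bias. The main gain from the change is removing discretion; the gain in precision is minor. The sample size of 12 is unaffected.

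**What to change.** Replace the protocol sentence, and add to the SAP:

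> For each direction, the mean of all valid trials (up to five) is analysed, for movement time and every other kinematic variable. A trial is excluded only for a fault on a closed list (loss of a required marker, false start, recording failure), judged on coded files without knowledge of group or result.

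Then add:
- A reach that misses the target is not a fault. It is kept for the variables it still defines, has no movement time, and is counted by group and direction.
- State the minimum number of valid trials per direction.
- Analyse with a mixed model, so that a participant with no valid time in one direction is not dropped from the others. A complete-case ANOVA would lose that person, one of an assumed six.
- Add a sensitivity analysis for unsuccessful reaches, because their times are not missing at random.

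The team may change the fault list, but must close it before seeing the data. Both documents describe the analyses in the past tense, so three trials may already have been used. In that case, state the rule applied and report the all-valid-trials result as a sensitivity analysis.

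Cost: two more reaches per direction to process, 12 × 3 × 2 = 72 in total or 6 per participant, assuming they were recorded. It also needs coded files or a second person, and one paragraph in each document. An atypical first or last trial may enter the mean.
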